## 4.7 Study Agent

Name of the medication-Hydroxychloroquine (Off label use)

Hydroxychloroquine- The full prescribing information can be accessed at:

<https://dailymed.nlm.nih.gov/dailymed/drugInfo.cfm?setid=b82bbda6-64f2-4426-b4ec-254eeea895ae>

Subjects will obtain the study drug in accordance with established SOP from the hospital-based pharmacy.

### 4.7.1 Disallowed Concomitant Therapy

See attached appendix of exclusionary and potentially exclusionary medications

#### 4.7.1.1 Dose Rationale

Hydroxychloroquine is a long-acting drug (elimination half-life:50 days). Loading dose of HCQ 600 mg has been administered for rheumatoid arthritis or systemic lupus erythematosus, with a usual maintenance dose 200 mg. Since the protocol will be used in HCWs with at high risk of exposure to SARS-CoV-2, the intent is to rapidly achieve an adequate drug level. For this study, we selected a loading dose of 600 mg on day one followed by 200 mg for daily maintenance dose.

#### 4.7.1.2 Administration

- Loading dose: 600 mg, oral, 1 day
- Maintenance dose: 200 mg, oral, daily, for 90 days

The study will follow the study agent's labeling guidelines except the dosing schedule selected as described above.

#### 4.7.1.3 Supplies

HCQ will be dispensed at the time of study enrollment or as soon as practical thereafter, after subjects have completed all Screening procedures and signed informed consent. The drug will be requested from the UNMH Research Pharmacy on the 4th floor or other approved clinical trial pharmacy locations where it may be stored. Drug will be dispensed to subjects by qualified study personnel. There will be no cost to the participants. Currently there is a sufficient amount of HCQ. This study will not deplete HCQ from stores or pharmacies. HCQ supplies for standard of care and patients with preexisting indications will not be compromised by execution of this study.

Dispensing schedules

- 33 pills (200 mg oral tablet) at enrollment
- 30 pills (200 mg oral tablet) at 30 and 60 day visits

## 5 Study Procedures and Schedule

### 5.1 Study Procedures/Evaluations

#### 5.1.1 Study Specific Procedures

##### Employee Exposure Survey and Aerosol Generating Procedures (Appendix A)

Participants from both Group A and B will be asked to complete the Employee Exposure Survey. This online instrument asks health care providers currently working in at risk units to report symptoms or exposures (eg. AGPs) related to their encounters with patients who have or are suspected of Covid-19. These HCWs are reminded to complete the Survey once per day. The link to this REDCap survey is currently being emailed to UNMHSC HCWs and they can access it through widely distributed QR codes. Given its active use, this survey will not add additional stress or workload to study participants. Additional study specific questions will be added to this survey and the data is linked to REDcap a database.

Confirmation of Pregnancy in Women of Childbearing Potential: We will document in subject's research record whether they are pregnant based on self-report and date of last menses (at Screening and follow-up visits). Pregnancy is not a contraindication for receiving HCQ.

A list of potential Aerosol Generating Procedures (AGP) is also provided in Appendix A.

Subjects will only be asked to complete SARS-CoV-2 testing at study enrollment and the 30, 60 and 90 day follow up points, with a 7-day window after each time point to complete the testing.

### 5.2 Study Schedule

#### 5.2.1 Schematic of Study Design

##### Schematic of Study Design

**Schedules of Activities for COVID-19 HCWP HCW HCQ Study**

Task	Screening/ Baseline	Daily (existing required survey)	30 Day (± 7days)	60 Day (± 7days)	90 Day (± 7days)	Early Termination or Clinically Suspected SARS- CoV-2
Consent	X					
Health history	X					
Exposure Survey (online)	X	X				X
Swab* for SARS-CoV-2 and plasma/serum sample	X		X	X	X	X
Hydroxychloroquine dosing initiation	X					
Adverse Events		X	X	X	X	X

\*Lab has confirmed ability to test samples from week over next weekend. Estimate up to 50 total per week (25 Sat, 25 Sun). Lab has also agreed to bank plasma and serum samples for delayed analysis.

#### 5.2.2 Screening and Enrollment Visit

Both Screening and Enrollment visits can occur on the same day. Participants will be assessed for study eligibility through a pre-screening visit which may be conducted via telephone and include completion of the Employee Exposure Survey. Those who decide to take HCQ will be the experimental group (Group A), and participants who choose not to take HCQ will be part of the control group (Group B).

The Employee Exposure Survey can be accessed online via the following URL: <https://is.gd/reportexposure>. It can also be accessed by this QR code placed strategically in relevant patient care areas:

A hard copy of the survey is also attached as an appendix at the end of this protocol document. Questions relevant to this study will be added to the survey if the respondent indicates they are a study participant. We will use the REDcap database to track adherence to the protocol required surveys and send email or phone reminders if more than 2 days are missed.

### **5.2.3 Visit for Switching from Group B to Group A**

This study will allow participants to switch from Group B to Group A. If the previous visit is more than 7 days, survey collection will be done at the time of switch over. Switched participants will follow the study agent administration described in 4.7.1.2. Participants will be rescreened using screening form at the time of switch.

- Group A: approximately up to 275 (HCW choose to be provided HCQ)
- Group B: approximately up to 75 (HCW choose not to be provided HCQ)

Subjects who switch from Group B to Group A will not be replaced.

### **5.2.4 Early Termination Visit**

Early termination visit will consist of questionnaire and nasal swab.

## **5.3 Laboratory Procedures/Evaluations**

Standard diagnostic swabs will be collected from the participants at baseline and at 30, 60, and 90 day follow up points (with a 7-day window after each time point to complete the testing). A portion of any participant sample testing positive for SARS-CoV-2 will also be evaluated with metagenomic next-generation sequencing. Only viral RNA will be sequenced, not human DNA/RNA.

The Executive Director of Research at the UNM Health Sciences Center Office of Research will be working with institutional officials to ensure the use of viral transport media and swabs during the study do not interfere with adequate supplies available for clinical use. A modification will be submitted to clarify who will supply the swabs and the transport media (i.e. TriCore, UNMH).

## **6 Assessment of Safety**

Participants will be asked about any potential side effects experienced during study period at the 30, 60, and 90 day visits. In addition, subjects will report any potential AE's as part of the modified, daily Employee Exposure Survey to be completed daily. All subjects are HCW's and a space will be included for them to enter any new symptoms they may have experienced. If none they will indicate none. In their busy, at-risk environment, enrolled HCW's will not be presented with a lengthy list of uncommon and rarely serious AE's reported with HCQ. Given concerns of cardiac toxicity (dysrhythmias) with the use of the study drug, particularly when combined with azithromycin, the following verbiage will be inserted into the informed consent form: "In addition, taking macrolide antibiotics (azithromycin, clarithromycin, erythromycin, spiramycin, telithromycin) while receiving hydroxychloroquine may increase the risk of serious heart rhythm problems (e.g. torsades de pointes). You may wish to consult with your physician before participating in the trial because you may be predisposed to these problems." The FDA warning about the use of hydroxychloroquine for treatment of COVID-19 (released April, 2020) will also be discussed in the consent form.

## 6.1 Definition of Adverse Events (AE)

An **adverse event** (AE) is any symptom, sign, illness or experience that develops or worsens in severity during the course of the study. Intercurrent illnesses or injuries should be regarded as adverse events. Abnormal results of diagnostic procedures are considered to be adverse events if the abnormality:

- results in study withdrawal
- is associated with a serious adverse event
- is associated with clinical signs or symptoms
- leads to additional treatment or to further diagnostic tests
- is considered by the investigator to be of clinical significance

All AEs will be recorded on eCRFs. All recorded AE's will have a severity grade as well as causality (related or not related to Hydroxychloroquine) as determined by an investigator.

## 6.2 Definition of Serious Adverse Events (SAE)

An SAE is defined as any untoward medical occurrence that:

- Results in death
- Is life-threatening
- Requires inpatient hospitalization or prolongation of existing hospitalization
- Results in persistent or significant disability/incapacity
- Is an important medical event that may not be immediately life-threatening or result in death or hospitalization but may jeopardize the patient or may require intervention to prevent one of the other outcomes listed in the definition above)

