Pregnant and /or lactating women will not be excluded from this study. HCQ is a standard of care for management of lupus and rheumatic diseases in pregnant women. There is an absence of data that the drug increases the rate of miscarriages or teratogenicity. Additionally, the drug is approved to be used in pregnant women to treat autoimmune disease and there is consensus in the scientific community that the drug does not have adverse effects on the fetus [13-16]. Each participant providing consent is fully informed regarding the reasonably foreseeable impact of the research on the fetus or neonate. No inducements, monetary or otherwise, will be offered to terminate a pregnancy; Individuals engaged in the research will have no part in any decisions as to the timing, method, or procedures used to terminate a pregnancy; and Individuals engaged in the research will have no part in determining the viability of a neonate. A systematic review determined that HCQ use was not associated with any increased risk of congenital defects, spontaneous abortions, fetal death, pre-maturity or decreased numbers of live births in patients with auto-immune diseases. (Systematic review of hydroxychloroquine use in pregnant patients with autoimmune diseases, *Pediatric Rheumatol Online J.* 2009; 7: 9).

Additionally, *Arthritis Rheum.* 2003 Nov;48(11):3207-11 published. Safety of hydroxychloroquine in pregnant patients with connective tissue diseases: a study of one hundred thirty-three cases compared with a control group. Hydroxychloroquine in systemic lupus erythematosus and rheumatoid arthritis and its safety in pregnancy. Appeared in *Expert Opin Drug Saf.* 2011 Sep;10(5):705-14.

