## 6.4 Time Period and Frequency for Event Assessment and Follow-Up

All AEs including local and systemic reactions not meeting the criteria for SAEs will be captured on the appropriate CRF. Information to be collected includes event description, time of onset, clinician's assessment of severity, relationship to study product (assessed only by those with the training and authority to make a diagnosis), and time of resolution/stabilization of the event. All AEs occurring while on study must be documented appropriately regardless of relationship.

Any medical condition that is present at the time that the participant is screened will be considered as baseline and not reported as an AE. However, if the study participant's condition deteriorates at any time during the study, it will be recorded as an AE and all AEs will be recorded in the data collection system throughout the study.

Changes in the severity of an AE will be documented to allow an assessment of the duration of the event at each level of severity to be performed. AEs characterized as intermittent require documentation of onset and duration of each episode.

The PI will record all reportable events with start dates occurring any time after informed consent is obtained until 7 (for non-serious AEs) or 30 days (for SAEs) after the last day of study participation. At each study visit, designated study personnel will inquire about the occurrence of AE/SAEs since the last visit. Events will be followed for outcome information until resolution or stabilization.

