## **10 Data Handling and Record Keeping**

### **10.1 Data Collection and Management Responsibilities**

- Participants will be assigned a randomly generated study ID that will be linked to identifiers (MRN, DOB) in a linking table to be kept separate from the research data. Data and specimens will be labelled with the study ID only.
- Only HRRC-approved members of the study team who have the appropriate training will have access to the data and identifiers.
- Data will be entered into REDCap on a password-protected computer using a secure network.
- Any hard copy records/data will be kept in a locked file cabinet in the locked office of a designated member of the study team
- The specimens will be kept and stored in the Clinical and Translational Science Center at the UNM HSC and can only be accessed by the members of the study team. Then specimens will be transported to TriCore Laboratory and can only be accessed by laboratory personnel for the purpose specified in the protocol.
- Once data collection is complete, data will be de-identified by destruction of the linking table. Study records will be kept for 6 years past study closure.
- Biological samples collected for the study (e.g. blood) will not be stored in a repository, but will be destroyed after analysis and after completion of the study.

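### Pregnant women may enrol, but the SAE list has no birth-defect criterion and no pregnancy is followed to outcome, so most birth outcomes have no defined route to the DSMB

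*Combined protocol and SAP*

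**What the plan says.** Section 4.2.1.3 states: "Pregnant and /or lactating women will not be excluded from this study". Section 5.1.1 provides for status only: "We will document in subject's research record whether they are pregnant based on self-report and date of last menses", at screening and at follow-up visits.

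Section 6.2 opens with a qualifier, "An SAE is defined as any untoward medical occurrence that", and then lists five criteria: death, threat to life, hospitalization ("Requires inpatient hospitalization or prolongation of existing hospitalization"), "Results in persistent or significant disability/incapacity", and a catch-all ("Is an important medical event that may not be immediately life-threatening or result in death or hospitalization but may jeopardize the patient"). Congenital anomaly or birth defect is not among them.

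Section 6.4 records new events from consent "until 7 (for non-serious AEs) or 30 days (for SAEs) after the last day of study participation". Events already recorded are followed until they resolve or stabilize. A condition present at screening is baseline and is not an AE unless it deteriorates. Section 10.1 adds: "Once data collection is complete, data will be de-identified by destruction of the linking table".

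No section provides for following a pregnancy to its outcome or for observing a newborn or a breastfed infant. None says how an admission for delivery is to be classed.

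**The concern.** The protocol gives an off-label prophylactic drug to asymptomatic workers, some of whom may be pregnant or become so. It identifies these women and then specifies nothing further. To justify enrolling them, section 4.2.1.3 cites evidence on birth defects, miscarriage, fetal death and prematurity, drawn from women treated for autoimmune or connective tissue disease. Those are the outcomes one would want recorded here too.

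If staff follow the SAE list and the recording window exactly, an anomaly found at birth after an exposed pregnancy has no defined place in the safety data. The DSMB described in 6.4.1 would then receive no anomaly reports whether or not any occurred, and the absence of reports would tell it little.

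**Working it through.** The plan states no figure on this point, so the check is date arithmetic plus a reading of the sections side by side.

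**Inputs from the protocol**
- Participation: up to 90 days (4.4).
- Last visit: up to 7 days after day 90 (5.1.1, 5.2.1).
- Recording of new SAEs: 30 days after the last day of participation (6.4).

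**Assumptions, not in the documents**
- Delivery at 40 weeks (280 days), with 37 weeks (259 days) as the lower end of term.
- Conception two weeks (14 days) after the last menstrual period.

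**Step 1. When recording closes.** Close = last day of participation + 30.
- 90 + 30 = day 120; 120/7 = 17.1 weeks.
- 97 + 30 = day 127; 127/7 = 18.1 weeks.

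**Step 2. Women pregnant at enrolment.** Delivery falls after the close if gestation at enrolment is less than (length of pregnancy − close).

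| Delivery at | Close at day 120 | Close at day 127 |
|---|---|---|
| 40 weeks | 280 − 120 = 160 days = 22.9 weeks | 280 − 127 = 153 days = 21.9 weeks |
| 37 weeks | 259 − 120 = 139 days = 19.9 weeks | 259 − 127 = 132 days = 18.9 weeks |

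So a woman enrolled in roughly the first half of pregnancy delivers after recording has closed. For example, enrolment at 8 weeks puts her at 8 + 17.1 = 25.1 weeks at the close, about 15 weeks before a 40-week delivery.

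**Step 3. Women who conceive on study.** The case most favourable to capture is conception on the day of enrolment. Gestation at the close is then 14 + 120 = 134 days = 19.1 weeks, or 14 + 127 = 141 days = 20.1 weeks. Both are well short of 37 weeks, so every term delivery in this group falls outside the window.

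**Step 4. Early termination.** A participant who leaves at day 30 has new SAEs recorded only to day 30 + 30 = day 60, so the gap widens. Section 4.6 allows several such exits, including a positive PCR.

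**Step 5. Do other provisions fill the gap?**
- The follow-up rule in 6.4 applies to recorded events. A pregnancy is not defined as one, and a pregnancy present at screening is baseline.
- The instruction in 6.3.2 to report in case of doubt works only if someone learns of the event. No contact is planned after the window.
- The catch-all in 6.2 refers to the patient. The other four criteria name no subject, so offspring are neither clearly included nor clearly excluded.

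**The case against.** Much of the safety system does reach the mother. The AE definition in 6.1 is broad. Section 6 adds a daily free-text entry and questions at the 30, 60 and 90 day visits, 6.3.2 says to report in case of doubt, and 6.4.1 gives the DSMB frequent review. A miscarriage, fetal death or preterm labour during participation happens to the participant and can be recorded as an AE, or as an SAE through the hospitalization, threat-to-life or catch-all criteria. This stands. A reader might infer that the trial cannot detect any fetal harm; the documents do not support that.

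A reader might also infer that every normal delivery admission is an SAE under "Requires inpatient hospitalization or prolongation of existing hospitalization". That does not follow, because the qualifier "An SAE is defined as any untoward medical occurrence that" comes first and an uncomplicated delivery is not plainly untoward. What remains is that no rule is written, so classification is left to judgement.

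Nor does section 4.2.1.3 present the pregnancy outcomes as concerns. It cites them as reassurance, reporting no increased risk. That weakens any charge that the protocol ignores a hazard it has itself identified, but it does not supply the missing follow-up.

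Destruction of the linking table is tied to the end of data collection, not to a participant's day 120. With a 12-month study, the table may outlast delivery for early enrollees. The problem arises only because pregnancy outcomes are not part of data collection as now defined.

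Finally, the manual of procedures and the consent form were not available for this check and could contain pregnancy procedures. The conclusion is therefore about what the protocol specifies.

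**Conclusion.** The point holds in a limited form. Pregnant and lactating women may enrol, the SAE list omits congenital anomaly or birth defect, and the protocol specifies no follow-up of pregnancy outcome. New SAEs stop being recorded at about day 120, or day 127 with the visit window. With delivery at 40 weeks, women enrolled before about 22 to 23 weeks' gestation deliver after that; with delivery at 37 weeks, the cut-off is about 19 to 20 weeks. Women who conceive on study and reach term all deliver after it. Congenital anomaly, neonatal outcome and any outcome after the window have no defined route to the DSMB.

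These cut-offs rest on the assumed lengths of pregnancy. The documents do not give the number of pregnancies expected, and the conclusion does not depend on it. A reader might infer that follow-up would let the DSMB establish or exclude an effect of the drug on birth defects. Nothing in the documents supports that: the sample size in 7.5 is set for PCR positivity among up to 350 participants, of whom pregnant women are an unstated part. The benefit is capture of individual cases. The primary endpoint and its analysis are not affected.

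**What to change.** **Section 6.2.** Add a criterion for congenital anomaly or birth defect, or fetal or neonatal death, in a participant's offspring. State that admission for an uncomplicated delivery is not in itself an SAE.

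**Section 6.4.** State that any pregnancy present at enrolment, or reported up to the end of the 30-day SAE window, is followed by remote contact to its outcome and reported to the DSMB. Apply this to both groups, so that outcomes are ascertained in the same way with and without the drug.

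**Section 10.1.** Make clear that data collection is not complete, and the linking table is kept, until those outcomes are recorded.

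**Cost.** A protocol amendment, matching consent wording, and a few remote contacts for each woman concerned. Section 5.1.1 already identifies the women and section 4.5 already makes visits after enrolment remote, so no new visit structure is needed. The downside is that some records, in a number the documents do not give, stay open and linked to identifiers past the main data lock.

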## 6.3 Classification of an Adverse Event (AE)

### 6.3.1 Severity of Event

For AEs not included in the protocol defined grading system, the following guidelines will be used to describe severity.

- **Mild** – Events require minimal or no treatment and do not interfere with the participant's daily activities.
- **Moderate** – Events result in a low level of inconvenience or concern with the therapeutic measures. Moderate events may cause some interference with functioning.
- **Severe** – Events interrupt a participant's usual daily activity and may require systemic drug therapy or other treatment. Severe events are usually potentially life-threatening or incapacitating.

### 6.3.2 Relationship to Study Agent

The clinician's assessment of an AE's relationship to study agent (drug, biologic, device) is part of the documentation process, but it is not a factor in determining what is or is not reported in the study. If there is any doubt as to whether a clinical observation is an AE, the event should be reported. All AEs must have their relationship to study agent assessed. In a clinical trial, the study product must always be suspect. To help assess, the following guidelines are used.

- **Related** – *The AE is known to occur with the study agent, there is a reasonable possibility that the study agent caused the AE, or there is a temporal relationship between the study agent and event. Reasonable possibility means that there is evidence to suggest a causal relationship between the study agent and the AE.*
- **Not Related** – *There is not a reasonable possibility that the administration of the study agent caused the event, there is no temporal relationship between the study agent and event onset, or an alternate etiology has been established.*

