### 3 Objectives

Primary Objective	Primary Endpoint
To evaluate the efficacy of hydroxychloroquine (HCQ) for prophylaxis to prevent severe acute respiratory syndrome coronavirus 2 (SARS-CoV-2) infection among HCWs at high risk of occupational exposure to SARS-CoV-2 compared to eligible cohort that declines treatment	Frequency of infection with SARS-CoV-2 as determined by positive PCR for the virus on standard diagnostic tests.
Secondary Objectives	Secondary Endpoints
1. To characterize whether high-risk HCW who test positive for SARS-CoV-2 have an asymptomatic infection or report symptoms of COVID-19 in the 4 weeks preceding positive SARS-CoV-2	1. Symptom questionnaires performed once daily as currently mandated for HCW in high risk settings within UNMHS.
2. Determine role of occupational health exposure risk level on subsequent conversion frequency (mild-moderate-severe)	2. Online survey required once daily for all at risk HCW (existing document)
3. To assess the severity of any SARS-CoV-2 infection after prophylactic treatment with hydroxychloroquine.	3. Symptom questionnaires, Hospital admission rate, ICU admission rate, Mortality rate, PSI score of respiratory compromise
4. To assess the tolerability of hydroxychloroquine prophylaxis of SARS-CoV-2 in this population	4. Incidence of AEs or SAEs related to HCQ at study termination.
Exploratory Objectives	Exploratory Endpoints
1. To determine whether hydroxychloroquine reduces time lost from work	1. Days away from work
2. To assess the compliance of hydroxychloroquine prophylaxis	2. Frequency of missing dose
3. To assess whether HCQ benefits are different for specific AGPs or exposure on certain covid units (MICU v. ED v. covid rule out unit)	3. Frequency of positive test for SARS-CoV-2 related to AGP's or specific Covid-19 units.
4. To compare seroconversion between HCQ-treated and HCQ-untreated subjects on blood or plasma specimens.	4. Serological analyses at 4 times points (baseline, 30,60 and 90 days of study enrollment---with a 7-day window after each time point to complete analyses)

5. Metagenomic next generation sequencing of SARS-CoV-2 isolates detected in subjects	5. Sequence of viral isolates compared to published genomes and community-circulating SARS-CoV-2
---	--

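### The Related and Not Related definitions overlap with no precedence rule, so the tolerability endpoint is not determined by its own rule and cannot separate drug effect from background symptoms

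*Combined protocol and SAP*

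**What the plan says.** Section 6.3.2 defines two causality categories, each a list of alternatives.

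- **Related**: the event is a recognised effect of the drug, or causation by the drug is reasonably possible, "or there is a temporal relationship between the study agent and event".
- **Not Related**: causation is not reasonably possible, or "there is no temporal relationship between the study agent and event onset, or an alternate etiology has been established".

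The section introduces these with "To help assess, the following guidelines are used" and states "In a clinical trial, the study product must always be suspect". It does not say which category prevails when both apply, and it gives no time window for a temporal relationship. Under section 6.1 an investigator assigns the category, and section 4.1 describes the study as open.

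In section 3, the endpoint for the tolerability objective (secondary endpoint 4) is "Incidence of AEs or SAEs related to HCQ at study termination". Section 7.4.3 names symptoms, hospital admission, ICU admission and mortality as secondary endpoints. It does not name adverse events, and no other part of section 7 specifies an adverse-event comparison.

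Capture is wider than the endpoint. Section 6.4 says: "All AEs occurring while on study must be documented appropriately regardless of relationship". Both groups complete the daily survey (section 5.1.1), and that survey carries the adverse-event items (section 6).

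**The concern.** A two-category flag works as an endpoint only if each event falls into one category. Here many events fall into both. HCQ is taken daily for 90 days (section 4.7.1.2) and has a stated elimination half-life of 50 days (section 4.7.1.1), so almost any Group A event after the first dose can be called temporally related. If the same event has another established cause, it is also Not Related. PCR-confirmed COVID-19 in a worker taking HCQ is an example: section 6.1 counts intercurrent illness as an adverse event, and this one satisfies both definitions.

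The endpoint also has no reference level. An event cannot be related to a drug that was never taken, so Group B participants who do not switch contribute nothing. Headache, fatigue and dyspepsia are common enough in working adults that an incidence in HCQ takers alone does not show how much the drug added. A reader of the final report could take a high figure as toxicity or a low one as good tolerability, when either might reflect how assessors read section 6.3.2.

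**Working it through.** The documents state no related-event rate to reproduce. The nearest figure is the rash expected in 1-2% of participants (section 2.2.1).

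**Step 1: do the definitions overlap?** Take four yes/no attributes from section 6.3.2: K (recognised effect of the drug), R (reasonable possibility), T (temporal relationship), A (alternate etiology established).

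- Related = K or R or T.
- Not Related = (not R) or (not T) or A.

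Over the 2 × 2 × 2 × 2 = 16 combinations:

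| | Both | Related only | Not Related only | Neither |
|---|---|---|---|---|
| All 16 | 12 | 2 | 2 | 0 |
| The 8 with T = yes | 6 | 2 | 0 | 0 |

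All 8 temporally related combinations meet Related, and 6 of them also meet Not Related. These are counts of logical cases, not of expected events.

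**Step 2: what are the two extremes?** If Related prevails in the overlap, every temporally related event counts, which for daily dosing is close to every on-treatment Group A event. If Not Related prevails, an event stays Related only when R and T hold and A does not. That leaves 2 of the 16 combinations.

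**Step 3: how far apart could the results be?** Inputs: Group A up to 275 and Group B up to 75 (section 4.2.1). Assumptions not in the documents: the 90-day background risk b of at least one adverse event is 10-50%; the HCQ-caused risk c is 2% (the top of the range expected for rash) or 10%; the two act independently. The proportion of Group A with any event is P = b + (1 − b)c. The excess over background is (1 − b)c.

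| b | c | P | Flagged by the temporal condition, 275P | With an HCQ-caused event, 275c | Excess (points) |
|---|---|---|---|---|---|
| 10% | 2% | 0.118 | 32 | 5.5 | 1.8 |
| 30% | 2% | 0.314 | 86 | 5.5 | 1.4 |
| 50% | 2% | 0.510 | 140 | 5.5 | 1.0 |
| 10% | 10% | 0.190 | 52 | 27.5 | 9.0 |
| 50% | 10% | 0.550 | 151 | 27.5 | 5.0 |

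For b = 10%, c = 2%: P = 0.10 + 0.90 × 0.02 = 0.118, and 275 × 0.118 = 32.

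**Step 4: how precise would an all-cause comparison be?** The 95% half-width of the difference, ignoring switching, is 1.96 × √[P(1 − P)/275 + b(1 − b)/75]. With c = 2%:

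- b = 10%: 1.96 × √(0.000378 + 0.001200) = 7.8 points.
- b = 30%: 1.96 × √(0.000783 + 0.002800) = 11.7 points.
- b = 50%: 1.96 × √(0.000909 + 0.003333) = 12.8 points.

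**The case against.** The strongest reply is that section 6.3.2 offers guidance to clinicians rather than an algorithm. Section 6.4 restricts the assessment to people trained and authorised to diagnose, and they would not call every coincident symptom drug-related. That stands against any claim that the endpoint will count nearly every Group A event. A reader might infer this from the temporal condition and from the instruction always to suspect the product, but it is only the upper bound, because the same overlap lets most of those events be called Not Related. The reply does not remove the problem: guidance that supports both answers leaves the endpoint to each assessor's habit, and the assessors know who takes HCQ.

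A second reply is that tolerability in treated people is a legitimate descriptive aim. The plan says so where it intends a comparison, as in the primary objective and exploratory objective 4, and sections 7.1 and 7.4.1 promise descriptive summaries of all data. This is fair: a zero in Group B follows from the endpoint's wording and is not an error in itself. But a descriptive related-event rate with no background rate beside it cannot show what HCQ added, and no by-group adverse-event table is specified.

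A third reply is that an all-cause comparison is itself weak. Participants choose their group (section 5.2.2), reporting is open, and switching from B to A is allowed (section 5.2.3). A half-width of 8-13 points cannot resolve an excess of 1-2 points. All of that stands and limits how the added comparison may be described.

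**Conclusion.** The point holds. The two causality categories overlap with no precedence rule, and secondary endpoint 4 rests on that classification alone. Its value can run from few events up to nearly all Group A events, depending on the condition applied. The overlap follows from the text and needs no assumption. The participant counts in the working rest on assumed background risks, and the 2% drug effect reflects rash only, although section 2.2.1 also mentions dyspepsia.

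Two stronger readings are not supported. A reader might infer that the DSMB reviews are distorted too. Section 6.4.1 has the board review accumulated data and adverse events without limiting it to related ones, and section 6.3.2 says relatedness does not decide what is reported. A reader might also infer that there are no control data. The endpoint lacks a comparator, but all-cause events are recorded in both groups.

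This should be corrected because a named secondary endpoint is not determined by its own rule. It does not affect the primary endpoint.

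**What to change.** 1. In section 6.3.2, make the two categories mutually exclusive, so that a temporal relationship alone does not suffice for Related and every event has one classification.
2. In secondary endpoint 4 and section 7.4.3, add the incidence of all-cause AEs and SAEs by group, with the between-group difference and 95% CI. For B-to-A switchers, split time before and after HCQ start and state the denominator for each part.
3. Keep relatedness as a descriptive table for HCQ takers.
4. Label the between-group difference descriptive. It is non-randomised, open-label and imprecise, and should not be presented as an unbiased estimate of the drug's effect.

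The cost is protocol and SAP wording plus some programming for the switchers. No new data collection is needed, since all adverse events are already to be recorded and both groups complete the daily survey. The downside is the wide interval, about 8-13 points either side at 275/75 under the assumed background risks.
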